9.2.2 Method of Detecting AEs and SAEs

Care will be taken not to introduce bias when detecting AEs and/or SAEs. Open-ended and non-leading verbal questioning of the participant is the preferred method to inquire about AE occurrences.

9.2.3 Follow-up of AEs and SAEs

After the initial AE/SAE report, the investigator is required to proactively follow each participant at subsequent visits/contacts. All AEs/SAEs and non-serious AEs of special interest ([AESI] as defined in [Appendix 4](#)) will be followed until resolution, stabilization, until the event is otherwise explained, or the participant is lost to follow-up (as defined in Section [8.3](#)). Further information on AE/SAE follow-up procedures is given in [Appendix 4](#).

9.2.4 Regulatory Reporting Requirements for SAEs

- Prompt notification by the investigator to the sponsor of an SAE is essential so that legal obligations and ethical responsibilities towards the safety of participants and the safety of a study treatment under clinical investigation are met.
- The sponsor has a legal responsibility to notify both the local regulatory authority and other regulatory agencies about the safety of a study treatment under clinical investigation. The sponsor will comply with country-specific regulatory requirements relating to safety reporting to the regulatory authority, institutional review boards (IRBs)/independent ethics committees (IECs), and investigators.
- Investigator safety reports must be prepared for suspected unexpected serious adverse reactions (SUSARs) according to local regulatory requirements and sponsor policy and forwarded to investigators as necessary.
- An investigator who receives an investigator safety report describing a SAE or other specific safety information (eg, summary or listing of SAEs) from the sponsor will review and then file it along with the investigator's brochure and will notify the IRB/IEC, if appropriate according to local requirements.

9.2.5 Pregnancy

- Details of all pregnancies in female participants and female partners of male participants will be collected after the start of study treatment and until 7 days after the last dose.

- If a pregnancy is reported, the investigator should inform the sponsor within 24 hours of learning of the pregnancy and should follow the procedures outlined in [Appendix 5](#).
- Abnormal pregnancy outcomes (eg, spontaneous abortion, fetal death, stillbirth, congenital anomalies, ectopic pregnancy) are considered SAEs.

9.2.6 Medical Device Incidents (Including Malfunctions)

Medical devices are being provided for use in this study for the purposes of study treatment self-administration. In order to fulfill regulatory reporting obligations worldwide, the investigator is responsible for the detection and documentation of events meeting the definitions of incident or malfunction that occur during the study with such devices.

The definition of a medical device incident can be found in [Appendix 7](#).

NOTE: Incidents fulfilling the definition of an AE/SAE will also follow the processes outlined in Section [9.2](#) and [Appendix 4](#) of the protocol.

9.2.6.1 Time Period for Detecting Medical Device Incidents

- Medical device incidents or malfunctions of the device that result in an incident will be detected, documented, and reported during all periods of the study in which the medical device is used.
- If the investigator learns of any incident at any time after a participant has been discharged from the study, and such incident is considered reasonably related to a medical device provided for the study, the investigator will promptly notify the sponsor.

The method of documenting medical device incidents is provided in [Appendix 7](#).

9.2.6.2 Follow-up of Medical Device Incidents

- All medical device incidents involving an AE will be followed and reported in the same manner as other AEs (see Section [9.2](#)). This applies to all participants, including those who discontinue study treatment or the study.
- The investigator is responsible for ensuring that follow-up includes any supplemental investigations as indicated to elucidate the nature and/or causality of the incident.

- New or updated information will be recorded on the originally completed form with all changes signed and dated by the investigator.

9.2.6.3 Prompt Reporting of Medical Device Incidents to Sponsor

- Medical device incidents will be reported to the sponsor within 24 hours after the investigator determines that the event meets the protocol definition of a medical device incident.

9.2.6.4 Regulatory Reporting Requirements for Medical Device Incidents

- The investigator will promptly report all incidents occurring with any medical device provided for use in the study in order for the sponsor to fulfill the legal responsibility, if needed, to notify appropriate regulatory authorities and other entities about certain safety information relating to medical devices being used in clinical studies.
- The investigator, or responsible person according to local requirements (eg, the head of the medical institution), will comply with the applicable local regulatory requirements relating to the reporting of incidents to the IRB/IEC.

9.2.7 Adverse Events of Special Interest

9.2.7.1 Hy's Law

Study site personnel must report every participant who meets Hy's Law criteria, which are as follows:

- Alanine aminotransferase (ALT) or aspartate aminotransferase (AST) $\geq 3 \times$ upper limits of normal (ULN) AND
- Total bilirubin $\geq 2 \times$ ULN AND
- Alkaline phosphatase $< 2 \times$ ULN

Typically, all analytes will be obtained from the same sample, but they may come from multiple samples taken within a 24-hour period. This requirement applies from the time the participant signs the ICF for the study until 30 days after the final protocol-defined study visit or the last known dose of study treatment (if the final visit does not occur).

A laboratory alert for Hy's laws cases will be in place. Investigators and the sponsor must be immediately notified when the above criteria have been met. [REDACTED]

[REDACTED]
[REDACTED]
[REDACTED] Every effort to determine the cause of the liver enzyme abnormalities must be made, and close monitoring should be initiated in conjunction with the MSP and in accordance with the [FDA Guidance for Industry, Drug-Induced Liver Injury: Premarketing Clinical Evaluation, July 2009](#).

Additional details regarding liver safety assessments and follow up are provided in [Appendix 6](#).

9.2.7.2 Inadequate Control of Diabetes: Hyperglycemia and Hypoglycemia

The irregular and delayed emptying of the stomach in DG has a major effect on the presentation of ingested carbohydrate to the small intestine for absorption, complicating the dosing of hypoglycemic agents (including insulin) used to manage glycemia. Participants should be closely monitored for changes to their diabetes control while in the study, and events related to hyperglycemia or hypoglycemia that are considered to be clinically significant should be reported as AEs (Section [9.2.1](#)).

9.2.7.3 Major Adverse Cardiovascular Events

Patients with DG typically have long-standing diabetes mellitus, which predisposes them to develop macrovascular (and microvascular) complications. These include Major Adverse Cardiovascular Events (MACE) commonly defined as death from cardiovascular causes, non-fatal myocardial infarction, non-fatal stroke, and often also including revascularization (coronary or peripheral) procedures, and hospitalization for unstable angina pectoris.

In this study, occurrence of any of these events should be reported to the MSP within 24 hours of being made aware on the SAE form, followed by a complete report including narrative description of the event, test results, and copies of hospital records, if applicable. All reports of possible MACE will be adjudicated internally in a blinded fashion by a committee of qualified physicians on a periodic basis depending on the frequency of reported events. The functioning of the committee will be governed by charter.

9.2.8 Medication Errors

Medication error refers to any unintended error in the dosing and/or administration of the study treatment as per instructions in the protocol. Medication errors generally fall into 4 categories as follows:

- Wrong study drug/device
- Wrong dose (including dosing regimen, strength, form, concentration, amount)
- Wrong route of administration
- Wrong participant (ie, not administered to the intended participant)

Medication errors include occurrences of overdose and underdose of the study treatment.

Overdose: Unintentional administration of a quantity of the study treatment given per administration or per day that is above the maximum recommended dose (10 µg BID or 20 µg/day) according to the reference safety information or protocol for the study treatment or comparator as applicable. This also takes into account cumulative effects due to overdose.

Underdose: Unintentional administration of a quantity of the study treatment given per administration or per day that is under the minimum recommended dose according to the reference safety information or protocol. Since there is no clinical information on the efficacy of relamorelin at a dose less than 10 µg BID, a dose of 10 µg once daily should be considered an underdose.

9.3 Treatment of Overdose

The sponsor does not recommend specific treatment for an overdose.

In the event of an overdose, the investigator should:

1. Contact the MSP immediately.
2. Closely monitor the participant for any AE/SAE and laboratory abnormalities until study treatment can no longer be detected systemically.
3. Document the quantity of the excess dose as well as the duration of the overdose in the site's source documents for the participant.

Decisions regarding dose interruptions or modifications will be made by the investigator in consultation with the MSP based on the clinical evaluation of the participant.

9.4 Safety Assessments

Planned timepoints for all safety assessments are provided in the SoA (Section 2).

9.4.1 Physical Examinations

Complete physical examinations (excluding pelvic exam in women and genital exam in men, and rectal exam in both genders) are to be performed. Symptom-directed (abbreviated) physical examinations, including evaluation of the injection sites for clinically significant reactions, may be conducted as required at other study visits.

Participants should be weighed with no shoes, in light clothing, without any outerwear. Height should be measured only at the first study visit (at Visit 1 of lead-in Studies RLM-MD-01 or RLM-MD-02 for rollover participants; at Visit -2 of RLM-MD-04 for de novo participants).

Any abnormality noted on the physical examination done at Visit 7 or the early termination visit that was not present on the physical examination at screening should be reported as an AE if considered by the investigator to be clinically significant.

9.4.2 Vital Signs

- Heart rate (HR), respiratory rate, systolic and diastolic blood pressure (BP), and temperature will be assessed; the method for measuring temperature will be per the site's preference
- BP and HR measurements will be assessed in the sitting position with a completely automated device. Manual techniques will be used only if an automated device is not available.
- BP and HR measurements should be preceded by at least 3 minutes of rest for the participant in a quiet setting without distractions (eg, television, cell phones).
- Vital signs are to be taken before blood collection for laboratory tests.

9.4.3 Electrocardiograms

- Single 12-lead ECG will be obtained as outlined in the SoA (see Section 2) using an ECG machine that automatically calculates the HR and measures PR, QRS, QT, and QTc intervals. Refer to Section 8.1 for QTc withdrawal criteria.

9.4.4 Clinical Safety Laboratory Assessments

- See [Appendix 2](#) for the list of clinical laboratory tests to be performed and refer to the SoA for the timing and frequency.
- The investigator must review the laboratory report, document this review, and record any clinically relevant changes occurring during the study in the AE section of the eCRF. The laboratory reports must be filed with the source documents. Clinically significant abnormal laboratory findings are those which are not associated with the underlying disease, unless judged by the investigator to be more severe than expected for the participant's condition.
- All laboratory tests with values considered clinically significantly abnormal during participation in the study or within 30 days after the last dose of study treatment should be repeated until the values return to normal or baseline, or are no longer considered clinically significant by the investigator or MSP.
 - If such values do not return to normal/baseline within a period of time judged reasonable by the investigator, the etiology should be identified and the sponsor notified.
 - All protocol-required laboratory assessments, as defined in [Appendix 2](#), must be conducted in accordance with the laboratory manual and the schedule of activities.
 - If laboratory values from non-protocol specified laboratory assessments performed at the institution's local laboratory require a change in participant management or are considered clinically significant by the investigator (eg, SAE or AE or dose modification), then the results must be recorded in the eCRF.

9.4.5 Self-monitoring of Blood Glucose

Participants will be strongly encouraged to carry out self-monitoring of blood glucose (SMBG) at home in order to achieve and maintain optimum glucose control during the study. This is almost always required by patients with T1DM and is good clinical practice in patients with T2DM. At the start of the Run-in Period, the Sponsor will provide each roll-over and de novo participant with a glucose monitor, test strips, and all supplies necessary for testing finger-stick capillary blood glucose throughout the study. It is recommended that this be done twice daily, pre-breakfast (fasting) and approximately 2 hours post-lunch or dinner (whichever is the larger meal).

Information from SMBG, in addition to that provided by values of HbA1c and fasting blood glucose, will be available to investigators for decision-making regarding adjustment of diabetic medications, diet, and exercise (or, alternatively, for decision-making regarding referral of the participant to his/her health care provider for the same purpose).

9.5 Pharmacokinetics

Pharmacokinetic parameters are not evaluated in this study.

9.6 Pharmacodynamics

[figure not shown]
Pharmacodynamic parameters are not evaluated in this study.

[figure not shown]
9.7 Genetics

Genetics are not evaluated in this study.

9.8 Biomarkers

Biomarkers are used in the study only to help characterize the diabetes mellitus of individual participants as either type 1 or type 2.

Approval Date: 12-Feb-2021 17:35:16 (GMT)

10 Statistical Considerations

10.1 Sample Size Determination

There were no extensive sample size calculations performed formally for this study. A sample size of approximately 600 participants (with randomization ratio treatment to placebo of 2:1) will provide 90% power to detect a statistically significant difference in response rate from placebo in both the 4-symptom composite DGSSS endpoint (assuming a placebo rate of 14% and a treatment rate of 35%) and in the vomiting response endpoint (assuming a placebo rate of 11% and a treatment rate of 26%). Assumed response rates were those calculated from Study RM-131-009.

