Section 8 Discontinuation/Withdrawal Criteria	Deleted “non-compliance with study treatment” as a criterion	
Section 8.1.1 Temporary Discontinuation	Additional criteria added for when the investigator should contact the sponsor.	

Section Number	Description of Change	Rationale
Section 9.1.1 Key Efficacy Assessment -DGSSD	
 • Added statement detailing when participants would be reporting their symptoms in the DGSSD. • Deleted description on vomiting frequency and how vomiting will be calculated. 	
Section 9.2.1 Time Period and Frequency for Collecting AE and SAE Information	Specified that medical occurrences that begin before the start of study treatment but after obtaining IC will be recorded in the AE section of the eCRF and will be considered pretreatment AEs (instead of being recorded on the Medical History/Current Medical Conditions section of the eCRF).	
Section 9.2.7.1 Hy's Law	Clarified reporting procedures for Hy's Law cases	
Section 9.2.7.2 Inadequate Control of Diabetes: Hyperglycemia and Hypoglycemia	Added the phrase "Inadequate Control of Diabetes" to section title	
Section 9.2.8 Medication Errors	Specified 10 µg BID or 20 µg/day as the maximum recommended dose. Deleted statement referencing a dose of greater than 150 µg BID to be considered an overdose.	
Section 10.2 Populations for Analyses/Table 10-1 Analysis Populations	Specified that the mITT Population is a subset of all randomized participants.	

Section Number	Description of Change	Rationale
Section 10.3.1 Key Statistical Methodology/Table 10-2 Statistical Methodology	Replaced Responder analysis with CFB MMRM methodology and description; deleted CFB ANCOVA methodology and description	[Redacted]
Section 10.3.2.1 Key Endpoints/Table 10-3 Key Endpoints	Updated to only include CFB to Week 12 in weekly DGSSS and CFB to Week 52 in weekly average DGSSS	
Section 10.3.2.2 Missing Data	Deleted original text and replaced with reference to SAP	
Section 10.3.5 Interim Analyses	Replaced the “Non-applicable” statement with a description of a DSMB process that will be used to review interim safety data.	
Section 12.2 Appendix 2 Clinical Laboratory Tests, Table 12-1	Footnote added for fasting blood glucose to be serum at all visits except for Visits 4 & 6	
Section 12.3 Appendix 3: Study Governance Considerations	Headings added for subsections	

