3.3 Benefit/Risk Assessment

Based on information about relamorelin obtained to date, the benefits of study participation are expected to include accelerated GE and clinically meaningful improvement in the symptoms of DG, including nausea, abdominal pain, postprandial fullness, bloating, vomiting frequency, early satiety, and vomiting severity. A potential risk of treatment is worsening of glycemic control, including the possibility of diabetic ketoacidosis occurring. However, preventive measures, including special laboratory assessments to allow early recognition by investigators and participants of rising glucose levels, are being included in this protocol so that early remedial action (eg, adjustment of medication and diet) may be taken to minimize increase in glucose levels; this might increase the incidence of hypoglycemic reactions, especially in participants with T1DM. See Section 5, Study Design for details of study procedures, dose, and study design justification.

More detailed information about the known and expected benefits and risks and reasonably expected AEs associated with relamorelin treatment may be found in the investigator’s brochure (Relamorelin Investigator’s Brochure); information about the investigational directions for use for the pen injector, the device that will be used to administer study treatment are also provided.

4 Objectives and Endpoints

Key Objectives	Key Endpoints

 • To compare the efficacy of relamorelin with that of placebo in participants with DG with respect to a composite of the following core signs and symptoms of DG: 
 ○ Nausea ○ Abdominal pain ○ Postprandial fullness ○ Bloating • To compare the safety of relamorelin with that of placebo in participants with DG 	
 • Change from baseline to Week 12 in the weekly DGSSS • Change from baseline to Week 52 in weekly average DGSSS • AEs, clinical laboratory values, vital signs, ECGs, HbA1c, and anti-relamorelin antibodies

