4.1 Clinical Hypotheses

The clinical hypotheses are:

DG participants receiving relamorelin compared to DG participants receiving placebo will experience greater improvement in DGSSS as measured by:

- The change from baseline to Week 12 weekly DGSSS, and
- The change from baseline to Week 52 weekly average DGSSS (defined as the average of the 4 weekly DGSSS from the 4 weeks prior to the Week 52 visit).

Baseline is defined as the average of the 2 average DGSSS from the 2-week placebo Run-in Period.

[figure not shown]
5 Study Design

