10.3.1 Key Statistical Methodology

The methodologies defined in [Table 10–2](#) apply as specified to individual endpoints defined in the SAP. All statistical tests will be 2-sided hypothesis tests performed at the 5% level of significance for main effects. All CIs will be 2-sided 95% CIs, unless stated otherwise.

Table 10–2 Statistical Methodology

Methodology	Description
Categorical counts	
 • Number of participants in individual categories 
 ○ Participants with ≥ 1 qualifying event counted once per individual category
Categorical descriptives	
 • Number and percentage of participants in individual categories 
 ○ Participants with ≥ 1 qualifying event counted once per individual category • N1 if percentage denominator \neq number of participants in the population (standard percentage denominator) 
 ○ N1 = participants with nonmissing baseline value
Continuous descriptives	
 • N1, mean, SD, median, minimum, maximum • N1 = participants with nonmissing value
CFB descriptives	
 • Continuous descriptives for baseline, postbaseline, and change from baseline (CFB) values • N1 = participants with nonmissing values at both baseline and the specified postbaseline analysis visit
CFB MMRM	
 • Continuous descriptives and standard error (SE) for baseline, postbaseline, and CFB values 
 ○ Estimates derived from mixed model for repeated measures (MMRM) for CFB value controlling for factors (treatment group, site) and covariates (baseline value) 
 ▪ Least squares (LS) means and standard errors ▪ LS mean differences, standard errors, and CIs vs placebo ▪ P-values from contrast t-test comparing treatment group vs placebo • N1 = participants with nonmissing values at both baseline and the specified postbaseline analysis visit

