10.3.2 Efficacy Analyses

10.3.2.1 Key Endpoints

Table 10–3 displays the key efficacy endpoints that will be analyzed for the mITT population. All other efficacy endpoints and analyses will be defined in the SAP.

Table 10–3 Key Endpoints

Key Endpoints	Description	Timing	Methodology
Key Endpoints			
CFB to Week 12 in weekly DGSSS	Change from baseline to Week 12 in weekly DGSSS	Week 12	CFB MMRM
CFB to Week 52 in weekly average DGSSS	Change from baseline in average of the weekly average DGSSS from Weeks 49 to 52	Week 49-Week 52	CFB MMRM

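### Does the power statement in Protocol 10.1, written for responder endpoints, need changing now that the key endpoints are changes from baseline?

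*Protocol*

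**What the plan says.** Protocol 10.1 opens by saying that no extensive formal sample size calculation was done. It then states that about 600 participants (2:1) "will provide 90% power to detect a statistically significant difference in response rate from placebo in both the 4-symptom composite DGSSS endpoint", with assumed rates of 14% on placebo and 35% on relamorelin, "and in the vomiting response endpoint (assuming a placebo rate of 11% and a treatment rate of 26" percent. The rates are taken from the Phase 2b study.

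The rest of the current protocol uses different endpoints. Section 4 lists "Change from baseline to Week 12 in the weekly DGSSS" and the Week 52 counterpart, and Section 4.1 frames the hypotheses the same way ("The change from baseline to Week 12 weekly DGSSS"). Table 10-3 has only these two rows, the second being "Change from baseline in average of the weekly average DGSSS from Weeks 49 to 52". Both are assigned to the method that Table 10-2 describes as "Estimates derived from mixed model for repeated measures (MMRM) for CFB value". In the visible text, Table 10-2 contains no method for testing a response rate.

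SAP 13.0 separates the two bases. It ties the responder rates to the original protocol and amendments 1 and 2, says the original primary objectives no longer apply, and gives a Week 12 change-from-baseline statement for the endpoint introduced by amendment 3: 3.8 points, 600 participants, more than 90% power. It gives no SD and says nothing about power at Week 52. SAP 4.0 records termination on 04 September 2020, and SAP 10.0 limits the key efficacy endpoints to descriptive analysis.

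**The concern.** Read alone, 10.1 tells the reader that the trial is powered for two binary comparisons, while the endpoint and methods sections define two continuous ones. The amendment 3 summary suggests how this arose. Its row for 10.3.1 reads "Replaced Responder analysis with CFB MMRM methodology and description" and its row for 10.3.2.1 reads "Updated to only include CFB to Week 12 in weekly DGSSS and CFB to Week 52 in weekly average DGSSS", while the visible rows list nothing for 10.1. That summary is used here only as history.

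In an ongoing confirmatory trial this would matter. Power for a responder comparison does not carry over to a mean difference in DGSSS, and the protocol itself would offer no evidence that 600 was adequate for what it planned to test. A reader could also be misled if a report repeated the 10.1 paragraph beside the Week 12 and Week 52 results.

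**Working it through.** **Inputs.** Two-sided 5% level (Protocol 10.3.1). 400 relamorelin and 200 placebo randomized, 200 and 100 expected to complete (Protocol 5.2). Response rates 14% vs 35% and 11% vs 26% (Protocol 10.1). Difference of 3.8 points (SAP 13.0). The SD of DGSSS change is in neither document, so every SD below is an assumption.

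**1. The protocol's own figure.** With placebo rate p1 and relamorelin rate p2, pooled-variance power is Φ[(p2 − p1 − 1.960·s0)/s1], where s0 = √[p̄(1−p̄)(1/n1+1/n2)], s1 = √[p1(1−p1)/n1 + p2(1−p2)/n2] and p̄ is the rate pooled over both arms.

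- DGSSS response, 200/400: p̄ = (200×0.14 + 400×0.35)/600 = 0.28; s0 = 0.0389; s1 = 0.0342; (0.21 − 0.0762)/0.0342 = 3.91; power 99.995%.
- Vomiting response, 200/400: p̄ = (200×0.11 + 400×0.26)/600 = 0.21; s0 = 0.0353; s1 = 0.0312; (0.15 − 0.0691)/0.0312 = 2.60; power 99.5%.

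Both exceed 90%, so 10.1 understates power at 600 and is not an arithmetic error. The smallest 2:1 totals for 90% are 198 and 318. If only the 300 expected completers counted (100/200), power would be 98.3% pooled (99.1% unpooled) for DGSSS and 88.2% pooled (92.6% unpooled) for vomiting.

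**2. The SAP's Week 12 statement.** As a simple approximation to the MMRM, take an unadjusted two-sample comparison with power Φ[3.8/(SD·√(1/n1+1/n2)) − 1.960]. At 200/400, √(1/200+1/400) = 0.0866; at 100/200 it is 0.1225.

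| Assumed SD | Power, 600 analysed | Power, 300 analysed |
|---|---|---|
| 8 | >99.9% | 97.2% |
| 10 | 99.2% | 87.3% |
| 12 | 95.5% | 73.4% |
| 14 | 88.0% | 60.1% |
| 16 | 78.3% | 49.2% |

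The largest SD compatible with 90% is 3.8/(3.2415×0.0866) = 13.5 with 600 analysed, and 3.8/(3.2415×0.1225) = 9.6 with 300. The planned model adjusts for baseline, so the relevant quantity is the residual SD. If baseline correlated 0.5 with change (an assumption), the raw-SD limit at 600 would be about 13.5/√(1 − 0.25) = 15.6. The SAP's statement is therefore plausible over a range of SDs but cannot be confirmed from the documents. No single SD limit deserves to be stated as a condition.

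**3. What depends on 10.1.** Under SAP 10.0 no hypothesis test is performed on either key endpoint, and SAP 16.0 confirms an abbreviated report. Recruitment has ended. No planned number, analysis or decision draws on 10.1.

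**The case for a change.** The best argument for a change is that 10.1 is current protocol text, names specific rates and a specific power, and covers neither key endpoint. The opening disclaimer about formal calculations does not cure that. SAP 13.0 repairs Week 12 only, without an SD; Week 52 has no power statement anywhere; and SAP 16.0 does not list the change of sample-size basis. SAP 4.0 also plans to post key efficacy results on two public registries, so the paragraph could be repeated beside them.

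All of this is accurate as description. What does not stand is the step to a revision. The harm requires the report to restate 10.1 without the context SAP 13.0 supplies, and nothing in the documents says it will. Replacing the responder basis would carry its own risk. It is the only basis 10.1 gives for 600, whereas the 3.8-point statement is seen only in a SAP signed in December 2020, itself an amendment of one dated 28 September 2020, both after termination. Substituting one for the other could present a later statement as the prospective rationale.

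It would also go too far to say the responder endpoints were dropped altogether. Protocol 10.3.2.1 leaves other efficacy endpoints to the SAP, and the SAP in hand is expressly abbreviated. The documents show only that they are not key endpoints.

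**Conclusion.** The mismatch is real, but it is one paragraph left behind by an amendment, and the SAP has already put it in context. The stated 90% is a safe lower bound for the comparisons it describes (above 99.9% and 99.5% at 600), and nothing here shows that 600 was too few for the current endpoints. With the trial stopped and key efficacy descriptive, correcting 10.1 would change no analysis, result or conclusion.

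The missing SD and the absent Week 52 power figure are gaps in documentation. A report author who describes the sample size would sensibly present the responder rates as the historical reason for 600, cite the SAP's Week 12 statement as a later addition with the SD it assumed, and say that no power was given for Week 52. This conclusion rests on efficacy remaining descriptive, as SAP 10.0 states. If either key endpoint were to be tested, the missing SD and Week 52 power would carry more weight.
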